9.2 Symptomatic Pulmonary Embolism (PE)

When PE is clinically suspected, spiral CT of the pulmonary arteries and/or ventilation-perfusion lung scan will be obtained. If there is a new intraluminal filling defect of a segmental or more central pulmonary artery or a "high probability" perfusion defect, PE will be diagnosed. PE will be excluded if the spiral CT is normal or there are no perfusion defects. If the perfusion scan or CT scan is non-diagnostic, bilateral lower extremity ultrasound will be performed and PE will be diagnosed if there is new DVT (see next section). Ultrasound will be repeated after 7 \pm 2 days if there is no new DVT. Pulmonary angiography may be performed if there are equivocal findings and/or serial ultrasound testing is considered unsafe. To distinguish clinically important new PE events from minor symptoms of PE events that may have occurred prior to randomization, and from the clinical findings of micro-embolization that are commonly observed during thrombolytic therapy (e.g. transient pleuritic chest pain that resolves completely), investigation for PE during the first 10 days after enrollment is discouraged (in subjects in both study arms) in the absence of more significant clinical findings that suggest a new symptomatic PE event. Symptomatic PE events will be assessed during the 24-month study period and reported.

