4.3 Exclusion Criteria

Subjects meeting any of these criteria will be excluded (all times are relative to screening date):

- 1. Age less than 16 years or greater than 75 years.
- 2. Symptom duration > 14 days for the DVT episode in the index leg (i.e., non-acute DVT).
- 3. In the index leg: established PTS, or previous symptomatic DVT within the last 2 years.
- 4. In the contralateral (non-index) leg: symptomatic acute DVT a) involving the iliac and/or common femoral vein; or b) for which thrombolysis is planned as part of initial therapy.

- 5. Limb-threatening circulatory compromise.
- 6. PE with hemodynamic compromise (i.e., hypotension).
- 7. Inability to tolerate PCDT procedure due to severe dyspnea or acute systemic illness.
- 8. Allergy, hypersensitivity, or thrombocytopenia from heparin, rt-PA, or iodinated contrast, except for mild-moderate contrast allergies for which steroid pre-medication can be used.
- Hemoglobin < 9.0 mg/dl, INR > 1.6 before warfarin was started, or platelets < 100,000/ml.
- 10. Moderate renal impairment in diabetic patients (estimated GFR < 60 ml/min) or severe renal impairment in non-diabetic patients (estimated GFR < 30 ml/min).
- 11. Active bleeding, recent (< 3 mo) GI bleeding, severe liver dysfunction, bleeding diathesis.
- Recent (< 3 mo) internal eye surgery or hemorrhagic retinopathy; recent (< 10 days) major surgery, cataract surgery, trauma, CPR, obstetrical delivery, or other invasive procedure.
- 13. History of stroke or intracranial/intraspinal bleed, tumor, vascular malformation, aneurysm.
- 14. Active cancer (metastatic, progressive, or treated within the last 6 months). Exception: patients with non-melanoma primary skin cancers are eligible to participate in the study.
- Severe hypertension on repeated readings (systolic > 180mmHg or diastolic > 105mmHg).
- 16. Pregnant (positive pregnancy test, women of childbearing potential must be tested).
- 17. Recently (<1 mo) had thrombolysis or is participating in another investigational drug study.
- 18. Use of a thienopryridine antiplatelet drug (except clopidogrel) in the last 5 days.
- 19. Life expectancy < 2 years or chronic non-ambulatory status.
- 20. Inability to provide informed consent or to comply with study assessments (e.g. due to cognitive impairment or geographic distance).

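### Section 9.2 requires a CT defect and the fallback DVT to be new, but not the high-probability perfusion defect, so a residual PE from before randomization can count as a new event

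*Protocol*

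**What the plan says.** Section 9.2 of the protocol starts the work-up on clinical suspicion: "When PE is clinically suspected, spiral CT of the pulmonary arteries and/or ventilation-perfusion lung scan will be obtained". PE can then be diagnosed in three ways.

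- **CT:** "a new intraluminal filling defect of a segmental or more central pulmonary artery".
- **Lung scan:** a high-probability "perfusion defect, PE will be diagnosed. PE will be excluded if the spiral CT is normal or there are no perfusion defects".
- **Non-diagnostic CT or scan:** "bilateral lower extremity ultrasound will be performed and PE will be diagnosed if there is new DVT".

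The same section gives an aim, "To distinguish clinically important new PE events from minor symptoms of PE events that may have occurred prior to randomization", and acts on it by stating that "investigation for PE during the first 10 days after enrollment is discouraged" in both arms unless more significant findings point to a new event. Events are counted over the 24-month study period.

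Section 4.3 lists, as its exclusion for PE as such, "PE with hemodynamic compromise (i.e., hypotension". Neither the baseline evaluation in 4.5 nor the schedule in Appendix 14 includes lung imaging. Under 9.5, suspected events go to blinded adjudicators who work from an adjudication manual. Section 12.3 places outcome procedures and diagnostic criteria in a Manual of Procedures. Neither manual is part of the document.

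**The concern.** Two of the three routes carry a newness condition and the third does not. Subjects with PE at randomization are eligible unless hemodynamically compromised, and 9.2 acknowledges that such PE exists. A subject with a persisting perfusion defect from that PE who later has chest symptoms and a lung scan meets the stated criterion without any new embolus.

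Symptomatic PE is a listed safety outcome (section 9) and a recognised risk of the experimental procedure (18.3.4). Symptomatic VTE is compared formally between arms in 15.3.1 and is singled out for DSMB review in 15.5. Few events are expected: 15.1 assumes 2% for symptomatic PE at 3 months in the Control Arm. With so few events, a definition that admits old disease, and that varies with the test a site chose, weakens the outcome.

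**Working it through.** **1. The criteria side by side.** The grammar does not carry the newness condition across. The sentence reads "If there is a new intraluminal filling defect of a segmental or more central pulmonary artery or a" and then gives the scan criterion, which has its own article and its own adjective.

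| Route in 9.2 | Must the finding be new? | Same residual PE from before randomization, no new embolus, no new DVT |
|---|---|---|
| CT filling defect | Yes | Not diagnosed: the defect is not new |
| Fallback ultrasound | Yes (new DVT) | Not diagnosed |
| High-probability perfusion defect | Not stated | Diagnosed |

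The scan route cannot correct itself by exclusion either, because the scan excludes PE only when there are no perfusion defects. Since 9.2 allows CT and/or a lung scan, the same subject can be an event or a non-event according to the test used.

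**2. Who can carry an old defect.** Section 4.3 excludes PE as such only with hemodynamic compromise, and the aim stated in 9.2 presupposes that some subjects had PE before randomization. The protocol schedules no baseline lung imaging, so a comparison study exists only if one was done in routine care.

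**3. What the 10-day sentence does.** It limits when imaging is sought. It does not change the diagnostic criterion, and it does not apply to the rest of the 24 months.

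**4. How the neighbouring section handles it.** For recurrent DVT, 9.3 requires change against earlier imaging where this exists: a newly non-compressible vein, an extension of at least 10 cm, or a 4-mm increase in diameter. The Ultrasound Core Laboratory reviews the recent and last previous studies when a site reports new DVT in a limb with previous DVT. The lung-scan route has no counterpart.

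**5. Effect on precision.** Section 15.1 states that with 311 evaluable subjects per arm and 2% in each, the 95% interval on a difference of 0% covers ±2.4%. As a check, the Wald half-width is 1.96 × √(2 × 0.02 × 0.98 / 311) = 2.20%. Adding the continuity correction 1/311 = 0.32% gives 2.52%. The Newcombe method gives 2.45% with 6/311 per arm and 2.48% at exactly 2%. The stated figure lies within this range and is not disputed.

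The same Wald formula, for rates raised equally in both arms to assumed levels, gives:

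| Rate in each arm | Half-width |
|---|---|
| 2% | 2.2% |
| 3% (assumed) | 2.7% |
| 4% (assumed) | 3.1% |
| 5% (assumed) | 3.4% |

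**6. Effect on the contrast.** Suppose, for illustration only, true rates of 2% and 4%, and false events adding 1 percentage point in each arm. The rates become 3% and 5%. The ratio falls from 4/2 = 2.00 to 5/3 = 1.67, while the difference stays at 2 points. If false events can arise only in subjects without a true event, the rates are 0.02 + 0.01 × 0.98 = 2.98% and 0.04 + 0.01 × 0.96 = 4.96%, a difference of 1.98 points. Relative measures are attenuated and the absolute difference is essentially unchanged.

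**The case against.** The strongest reply is that the sentence in 9.2 is not the last step. Under 9.5, two blinded expert adjudicators review each suspected event, three meet if they disagree, and they follow a manual that may contain a newness test. The 9.2 text on early work-up also speaks of new PE, so a sensible adjudicator could read the condition into the scan criterion. Part of this stands: it makes misclassification less likely in practice and shows that the matter is one of drafting. It does not remove the point. The protocol states the criterion itself, an unseen manual cannot be assumed to override it, and blinding to allocation does not tell an old defect from a new one.

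A reader might go further in three ways that the documents do not support.

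- **A number of false events.** Any count needs the share of subjects worked up, the share scanned and the share with a residual defect. The documents give none of these. Setting such a count against 0.02 × 692 = 13.8 events would also mix a 3-month Control Arm rate with a 24-month window.
- **A hidden excess in the PCDT arm, or a bias toward one arm.** The rule is the same in both arms, randomization balances entry PE in expectation, and adjudication is blinded. Equal false events leave the absolute difference essentially where it was, and that is the scale on which 15.1 states its precision for a descriptive PE analysis.
- **A need to send scans without a comparison study to the ultrasound step.** That would miss true new PE without new DVT and would alter a diagnostic pathway, which the inconsistency does not require.

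**Conclusion.** The point holds as an inconsistency within 9.2. The lung-scan criterion lacks the newness condition that the other two routes carry, and this conflicts with the section's own aim. As written, a residual defect can be scored as a new symptomatic PE at any suspected episode over 24 months, and event status can turn on the choice of test.

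The size cannot be given; the widths in the working are for scale only. The description of the effect as non-differential noise assumes that work-up and choice of test do not differ by arm, and the documents give no figures on either. On that assumption event rates rise, the interval widens and relative comparisons move toward no difference, while the absolute difference stays essentially unbiased. The primary endpoint, PTS on the Villalta scale, is not affected. This is a minor point: the wording defect is certain, its practical consequence is not.

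**What to change.** In 9.2, reconcile the criteria for endpoint classification: count a high-probability perfusion defect as a PE event only if it is new compared with earlier lung imaging (scan or CT) where such imaging is available. Put the same condition in the adjudication manual. Where no earlier lung imaging exists, leave the classification to the blinded adjudicators on all the clinical information. The diagnostic pathway itself need not change.

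The cost is one phrase in the protocol and a matching entry in the manual. Sites would need to send any earlier lung imaging report with the suspected-event documents. No visit, test, treatment or sample size changes.

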6.2.5 Allowed Adjunctive Endovascular Techniques

The following adjunctive endovascular techniques may be used, per the guidelines below, as they are widely used in standard clinical practice to enhance the delivery of rt-PA into the clot or to prevent complications of PCDT (specifically, pulmonary embolism and early re-thrombosis):

 Retrievable IVC Filters: Retrievable IVC filters are commonly used by endovascular physicians to prevent peri-procedural PE in selected patients undergoing PCDT. In a large prospective registry of proximal DVT patients undergoing infusion CDT (without mechanical thrombectomy), symptomatic PE occurred in only 1.3% (49). Therefore, IVC filter placement is discouraged in patients undergoing Infusion-First PCDT (Technique C). However, for patients being treated with single-session PCDT (Techniques A and B, which involve more clot manipulation), there is sparse data to support or refute the use of IVC filters and limited evidence suggests that major PE can occur as a PCDT complication (67,68,87). Therefore, in ATTRACT, a retrievable Tulip filter (Cook Inc., Bloomington, IN) may be used at physician discretion if there is IVC and/or iliac vein thrombus and singlesession PCDT is being used.

- 2. Balloon Maceration, Aspiration Thrombectomy, Rheolytic Thrombectomy, and Infusion CDT: As in routine clinical practice, after initial PCDT the physician may inflate a standard angioplasty balloon within any residual thrombus to macerate it and increase its surface area in order to enable rt-PA delivery to otherwise-inaccessible parts of the thrombus (63). A standard 7-8 French catheter and/or the AngioJet Rheolytic Thrombectomy System may be used to aspirate residual venous thrombus in order to improve flow and thereby prevent the complication of early re-thrombosis. Additional rt-PA bolus doses (up to 5mg per session) may be given. If there is still significant obstructing thrombus after the use of these measures, the physician may initiate (or for Technique C patients, continue) a continuous rt- PA infusion via a multisidehole infusion catheter at 0.01 mg/kg/hr (maximum allowable dose 1.0 mg/hr) for a maximum of 24 hours for Techniques A and B, or for a total maximum infusion time (including previous infusion) of 30 hours for Technique C. In all cases, the total rt-PA dose given for the entire treatment (all sessions together) may not exceed 35mg.

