15.3.1 Symptomatic Venous Thromboembolism

The proportion of subjects who develop symptomatic VTE within 24 months post-randomization (subdivided according to whether the event was within the first 10 days, 11 to 30 days, 31 to 90 days, or 91 days to 24 months) will be compared between the two treatment groups using a stratum-adjusted Cochran-Mantel-Haenszel test.

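### Early PE work-up is discouraged below an undefined threshold, partly for a PCDT-specific reason, so early non-fatal PE may be under-ascertained, possibly more in the PCDT arm

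*Protocol*

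**What the plan says.** Section 9.2 opens with a general rule: "When PE is clinically suspected, spiral CT of the pulmonary arteries and/or ventilation-perfusion lung scan will be obtained". Non-fatal PE is then diagnosed from imaging. Later in the section comes a rule for the early period: "investigation for PE during the first 10 days after enrollment is discouraged (in subjects in both study arms"), with the condition "in the absence of more significant clinical findings that suggest a new symptomatic PE event". What counts as more significant is not defined.

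Two reasons are given for wanting to isolate new, clinically important PE. One is possible confusion with "minor symptoms of PE events that may have occurred prior to randomization". The other concerns thrombolysis itself, namely "the clinical findings of micro-embolization that are commonly observed during thrombolytic therapy".

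Other sections bear on this window:

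- Section 5.1 places PCDT within 3 days of randomization.
- Section 6.2.5, on single-session PCDT, says that "limited evidence suggests that major PE can occur as a PCDT complication".
- Section 15.3.1 compares symptomatic VTE between arms, "subdivided according to whether the event was within the first 10 days" or in one of three later periods.
- Section 3 describes the trial as open-label with blinded assessors. Section 9.5 has blinded adjudicators review suspected events.
- Section 12.6 states that the intensity of surveillance will be the same in both arms.

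**The concern.** The period in which work-up is discouraged contains the procedure and its aftermath, and it is also a period for which the VTE comparison is reported separately. The same instruction covers both arms, but its content is not fully symmetric. A PCDT patient with early chest symptoms has a benign explanation named in the protocol that a control patient, who receives no thrombolysis, in practice does not have. The decision is made by clinicians who know the allocation, against an unstated threshold.

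Blinded adjudication cannot correct this, because an episode never raised as suspected PE does not reach the adjudicators. At stake is how a low early PE rate in the PCDT arm should be read: as few events, or as few events looked for. PE is a named safety outcome and a recognized risk of the procedure (Sections 9 and 18.3.4), so the reader of the results needs to tell these apart.

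**Working it through.** **The protocol's own precision figure.** Section 15.1 takes 2% in each arm and 311 evaluable subjects per arm, and states a 95% confidence interval of ±2.4 points around a difference of zero.

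- Expected events: 0.02 × 311 = 6.2 per arm.
- Wald: 1.96 × √(2 × 0.02 × 0.98 / 311) = 2.20 points.
- Agresti-Caffo at 2%: 2.35 points. Newcombe with 6/311 in each arm: 2.45 points.

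The stated 2.4 lies among these standard variants, so it is reproduced. One uncounted event changes an arm's rate by 1/311 = 0.32 points.

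**What the protocol does not give.** There is no 10-day PE rate, no frequency of early chest symptoms and no detection fraction. The following only shows how the mechanism works. Assumptions: true control rate 2% (the 3-month figure, used as a stand-in), 311 per arm, and assumed shares d_C and d_P of true PEs detected in the control and PCDT arms.

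Observed rate = true rate × share detected, so observed risk ratio = true risk ratio × d_P / d_C.

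*Equal detection, true 2% vs 4%.* The risk ratio stays at 2.0. Power is for a simple two-proportion comparison at the two-sided 0.01 level that Section 15.3 sets for secondary tests.

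| Detected in both arms | Observed difference | Power |
|---|---|---|
| 100% | 4.0 − 2.0 = 2.0 points | 13% |
| 75% | 3.0 − 1.5 = 1.5 points | 9% |
| 50% | 2.0 − 1.0 = 1.0 point | 6% |

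*Lower detection with PCDT.*

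| True rates | d_C / d_P | Observed risk ratio |
|---|---|---|
| 2% vs 4% | 90% / 60% | 2.0 × 0.60/0.90 = 1.33 |
| 2% vs 4% | 100% / 50% | 2.0 × 0.50/1.00 = 1.00 |
| 2% vs 3% | 90% / 60% | 1.5 × 0.60/0.90 = 1.00 |

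Equal under-detection shrinks the absolute difference and the power but leaves the risk ratio alone. Only unequal detection moves the risk ratio, and it would move the other way if PCDT patients were investigated more readily. The detection shares apply to the events in the window compared; in a 3-month figure, events after day 10 would dilute the effect.

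**The two statements in 9.2 side by side.** The first ties imaging to clinical suspicion. The second discourages investigation in days 0-10 below a higher, unstated level. They can be read together, but where suspicion ends and more significant findings begin is left to each site.

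**The case against.** The strongest case on the other side has five parts.

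1. **The rule is conditional.** A reader might infer that sites are told not to look for PE for 10 days. The text does not support that: imaging on clinical suspicion remains the general rule, and the discouragement lapses when findings are more significant.
2. **One reason serves both arms and is sound.** Exclusion 6 in Section 4.3 removes only PE with hemodynamic compromise, and neither Section 4.5 nor Appendix 14 schedules baseline chest imaging. Early scans could therefore label old PE as new. If open-label clinicians scanned PCDT patients more readily, that error would count against PCDT.
3. **Early symptoms are not lost.** Section 13.5 sends non-serious adverse events through day 30 to the data coordinating center in both arms. The exemptions in Section 13.2.2 do not cover chest pain or dyspnea, and Section 11.1 reviews adverse and thrombotic events at the 10-day visit.
4. **The gravest cases count without imaging.** Section 9.4 attributes sudden unexplained death to PE.
5. **The endpoint is symptomatic, clinically important PE.** Transient symptoms of micro-embolization are left out on purpose, much as Section 9.1 treats urine discoloration after thrombectomy.

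All five stand, and they limit the point. A reader might also infer that the early comparison is biased toward showing no harm. The documents do not establish that, because it needs detection to differ by arm in a known direction. What remains is that an adverse-event entry for chest pain is not an adjudicated suspected PE, and the protocol does not clearly route an early episode that was not imaged to adjudication. The Manual of Procedures and adjudication manual are not shown and may say more.

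**Conclusion.** The point holds as a risk of under-ascertainment, not as demonstrated bias. The threshold for early PE work-up is undefined in the protocol, is applied by clinicians who know the allocation, and rests partly on a reason specific to thrombolysis. Early non-fatal PE may be missed, possibly more often with PCDT, and the equal-surveillance statement in Section 12.6 is stronger than Section 9.2 supports.

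No size can be attached from the documents. The tables above rest on assumed detection shares and a borrowed 3-month rate; they show only that, with about 6 expected control events, modest differences in detection could hide or alter a real difference. The consequence is confined to a secondary safety comparison. Section 15.1 calls the PE analysis descriptive, and the primary analysis is unaffected. A change is still worth making because it is cheap and because episodes never recorded as suspected PE are hard to classify afterwards.

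**What to change.** - **Section 9.2:** reconcile the imaging rule at the start with the early discouragement, so that sites read them the same way. How is a matter for the trial's clinical leads; no work-up rule is proposed here, and imaging decisions stay as they are.
- **Capture:** in both arms, require the existing Suspected VTE form for every new cardiopulmonary episode in days 0-10, whether or not it was imaged. Such episodes are already reportable as adverse events under Section 13.5.
- **Adjudication (Section 9.5):** add a category, assigned blind to allocation, for suspected PE that was not investigated.
- **Section 15.3.1:** report that count by arm beside confirmed PE for days 0-10. Any analysis that counts these episodes as PE should be labelled only as an extreme-case sensitivity analysis. Many will be transient symptoms that Section 9.2 deliberately leaves out, and counting them all would load against PCDT.

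Cost: a few more short forms per site, one adjudication category and one extra table. No imaging is added.

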9.3 Symptomatic Recurrent DVT

To increase the accuracy of diagnosing recurrent DVT, there will be standardized recording of

48

ATTRACT

[name]

the extent of thrombus (diameters of the common femoral vein and popliteal vein and the thrombus' proximal and distal extent) on the baseline (strongly recommended when the exam is performed locally) and 1-month follow-up (this information is required) ultrasound exams. When recurrent DVT is clinically suspected during follow-up, compression ultrasound of the proximal veins (popliteal vein to common femoral vein) will be performed and a Compression Ultrasound CRF documenting the exam will be transmitted by the Clinical Center to the DCC. If there was no DVT on the last ultrasound (or on the last venogram performed during follow-up) of the same leg, recurrent DVT will be diagnosed using the same criteria as that of a gualifying proximal DVT (Section 4.4). If a previous ultrasound or a follow-up venogram is available for comparison, recurrent DVT will be diagnosed if one of the following criteria is met: (a) there is a new noncompressible common femoral, femoral, or popliteal vein; (b) there is ≥ 10cm extension of thrombus margin (i.e. transition from not fully compressible to normal); or (c) there is a 4-mm increase in compressed thrombus diameter at the common femoral vein or popliteal vein (77,119,121-124). If these criteria are not met, DVT will not be diagnosed and, if there is still uncertainty about the presence of recurrent DVT (e.g. moderate or high clinical suspicion for recurrent DVT: non-diagnostic findings on ultrasound), the ultrasound should be repeated after 7 + 2 days, and judged by the same criteria. If the second test is not diagnostic for recurrence, DVT will be excluded. Venography or CT scan can be performed if, in the absence of diagnostic findings, clinical suspicion for recurrence is high or the ultrasound findings are equivocal. If the Clinical Center interpreted the study as either negative (no evidence of new DVT), or positive for DVT in a limb with no previous DVT, the Adjudication Committee will review the clinical information and Compression Ultrasound CRF and provide a final adjudication of the event. If the Clinical Center interpreted the study as positive for new DVT in a limb with previous documented DVT, or if there is difficulty with interpretation, the recent and last previous ultrasound studies will be reviewed by the Ultrasound Core Laboratory. Taking into account the Ultrasound Core Laboratory's review along with the clinical information and Compression Ultrasound CRF, the Adjudication Committee will then provide a final adjudication of the event. Symptomatic recurrent DVT will be assessed during the 24-month study period and reported. In the PCDT Arm, early (within 1 month) re-thrombosis of PCDT-treated vein segments will be distinguished from other recurrent DVT events.
